Using the IHI Framework for Going to Full Scale,⁶⁶⁻⁶⁷ this project will focus on sustainability and scalability. We will assess, maximize, and optimize intervention: (1) scalability (per the Intervention Scalability Assessment Tool⁶⁸); (2) sustainability (per the Program Sustainability Assessment Tool⁶⁹⁻⁷⁰) (3) feasibility, acceptability, and appropriateness to providers and systems (per the Acceptability of Intervention Measure,⁷¹ Intervention Appropriateness Measure,⁷¹ and Feasibility of Intervention Measure⁷¹); and (4) actual and recommended implementation strategies (via process mapping and implementation process/case notes).

Statistical power. Assumptions. We conducted a simulation study, allowing for variability in release dates, numbers eligible, and introducing a small intra-cluster correlation (ICC = .01). We assumed 43,000 eligible subscribers for Study 1, with 50% randomly assigned to CC. Based on last year's data, we assumed 6,000 eligible subscribers for Study 2. We expect that ~10% of the 6,000 ($n \sim 600$) will have past suicide attempt identifiable through CareSource claims data. We assumed a six-month risk of suicide attempt 0.05, but past 12-month claims data-identified suicide attempt increases this risk (i.e., .034 in absence of past-year suicide attempt, 0.204 with a past-year suicide attempt, odd ratio (OR) = 5), similar to SPIRIT. **Results.** We ran the simulation model 2001 times. Significance was assessed using a two-tailed type-I error level of 5%. Caring Contacts. We will have 85.6% power to detect an effect equivalent to an OR of 0.89. CC has been found to have much stronger effects than this in previous studies²² suggesting that we are adequately powered for CC. RRT. If we assume an intervention effect for Study 2 of 0.87 OR, we will have 88.3% power to detect this effect. For subscribers with a past year suicide attempt within Study 2 (who will be flagged to receive SPI), we will have 96.4% power to detect an OR of 0.63 (the OR detected for SPI in our previous trial, SPIRIT).⁴⁶ Having superadequate power for this test offsets concerns about providers potentially not providing SPI as instructed in this large, real-world study.

D. Material Inducements

Study 1

Provider focus groups: No material inducements will be provided for BH providers who engage in the focus groups. Providers will complete study-related procedures during work time and are typically not able to accept material inducements.

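### The risks assumed for the power simulation (.034 and .204) give an odds ratio of 7.28, not the stated 5; the plan should say which input was coded.

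*Combined protocol and SAP*

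**What the plan says.** The protocol's section C4 (Data Analysis), under Statistical power, lists the inputs to a simulation run 2001 times. The overall risk is given as "We assumed a six-month risk of suicide attempt 0.05". The same sentence splits it by attempt history: "i.e., .034 in absence of past-year suicide attempt, 0.204 with a past-year suicide attempt, odd ratio (OR) = 5", and likens the contrast to an earlier trial by the group. On prevalence it says "We expect that ~10% of the 6,000" will have a past attempt identifiable in claims, about 600 people. The sample sizes are stated as "We assumed 43,000 eligible subscribers for Study 1, with 50% randomly assigned to CC" and "we assumed 6,000 eligible subscribers for Study 2".

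Three powers follow: 85.6% for Caring Contacts (CC) at OR 0.89, 88.3% for Reports, Re-engagement, and Training (RRT) at OR 0.87, and 96.4% at OR 0.63 for Study 2 subscribers with a past-year attempt, who are flagged for SPI. The paragraph then relies on the last figure to offset the worry that providers may not deliver SPI as instructed.

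**The concern.** Two risks fix their odds ratio. A reader who checks the parenthesis finds that the stated ratio does not belong to the stated risks, so at least one of the three figures is wrong as written. These are the only outcome-risk inputs the plan gives for the simulation, and its code is not shown. A simulation of this kind can be coded either from two risks or from a baseline and an odds ratio, and the two choices no longer describe the same population.

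What is at stake is chiefly the flagged subgroup, because its control risk enters the SPI power directly and the plan leans on that power. The data and safety monitoring board is to approve the analysis plan before the study starts, and it should see assumptions that agree with one another.

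**Working it through.** **Inputs** (all from the Statistical power paragraph): p0 = .034 without a past-year attempt; p1 = .204 with one; stated OR = 5; overall risk .05; prevalence about 10%; two-sided 5% test.

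**1. The stated odds ratio.** OR = [p1/(1 − p1)] / [p0/(1 − p0)] = (.204/.796) / (.034/.966) = 0.2563 / 0.0352 = **7.28**. Risk ratio = .204/.034 = 6.00. The stated 5 is not reproduced.

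**2. Rounding.** With p0 between .0335 and .0345 and p1 between .2035 and .2045, the OR runs from 7.15 to 7.42.

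**3. Do the risks fit the other inputs?** 0.9 × .034 + 0.1 × .204 = .0306 + .0204 = .051, against .05 stated. The overall risk is exactly .05 at a prevalence of (.05 − .034)/(.204 − .034) = 9.4%. The risks therefore fit, and the OR is the odd one out.

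**4. Where might 5 come from?** The excess relative risk is (.204 − .034)/.034 = 5.0. The odds of .204 against the overall .05 give 0.2563/0.0526 = 4.87. Neither is the contrast that the sentence describes.

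**5. What OR = 5 would imply.** With p1 = 5o/(1 + 5o), where o = p0/(1 − p0), and overall risk = 0.9 p0 + 0.1 p1:

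| Held fixed | p0 | p1 | Overall risk at 10% |
|---|---|---|---|
| p0 = .034 | .034 | .150 | .046 |
| p1 = .204 | .049 | .204 | .064 |
| Overall = .05 | .037 | .163 | .050 |

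In the last row, a prevalence of 8% to 12% moves p1 from .171 to .156.

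**6. Sensitivity of the flagged subgroup (illustrative).** Assume 300 unexposed and 300 exposed, no clustering, and a two-proportion z-test at OR 0.63. Then q = 0.63·odds(p)/(1 + 0.63·odds(p)) and power = Φ[(p − q − 1.96·SE0)/SE1], with pooled SE0 and unpooled SE1.

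| Control risk p | Exposed risk q | Expected attempts in 300 unexposed | Power |
|---|---|---|---|
| .204 | .139 | 61 | 56% |
| .163 | .109 | 49 | 48% |
| .150 | .100 | 45 | 46% |

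None of these approaches the stated 96.4%. The table shows direction and rough sensitivity only.

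**7. Sensitivity of the other two powers.** A Wald approximation stratified by attempt history uses power = Φ(|ln OR|·√I − 1.96), where I sums 1/[1/(n₀p(1 − p)) + 1/(n₁q(1 − q))] over the two strata; n₀ and n₁ are the unexposed and exposed numbers, split 1:1.

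- CC, 43,000, OR 0.89: 71.3% with .034/.204; 71.5% with .037/.163; 67.8% with .034/.150; 81.0% with .049/.204.
- RRT, 6,000, OR 0.87, assumed 50% exposure and no clustering: 20% with .034/.204 and 20% with .037/.163.

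These do not reproduce 85.6% or 88.3% either. With the overall risk held at .05, neither figure moves materially between the two sets of inputs.

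**The case against.** The best defence is that this is a slip of labelling with no effect on any result. The two risks agree with the overall risk and the approximate prevalence, and 5 is exactly their excess relative risk. If the risks were what was simulated, every stated power is untouched by this point. That argument stands as the likelier account. It remains an inference, because the code is not given, and even if it is right the printed odds ratio still needs correcting.

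Two other defences do not rescue the 5. Rounding cannot reach it. Nor can the intra-cluster correlation of .01: it is too small to matter, and a cluster-conditional odds ratio would lie further from 1 than the marginal one, not nearer.

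A reader might go further and infer that the mismatch undermines all three powers, or explains why a simple calculation gives 56% where the plan states 96.4%. The documents do not support either reading. CC and RRT barely move while the overall risk stays at .05. The 56% is obtained with the plan's own risk of .204, so its distance from 96.4% cannot come from the odds ratio. The plan's figure comes from a simulation whose code and full model are not shown, and its SPI hypothesis is tested through an interaction in a model of all 43,000 subscribers, not by a two-group test in 600.

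A reader might also take .037/.163 as the correct pair. It is only one of several that fit OR = 5. It needs an overall risk of exactly .05 and a prevalence of exactly 10%. The plan gives the 10% only approximately, only for Study 2, and for a past attempt identifiable in claims without limiting it to the past year.

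**Conclusion.** The inconsistency is certain and rests on nothing but the plan's own figures: the odds ratio implied by .034 and .204 is 7.28, not 5. The odds ratio is probably the wrong entry, but this cannot be settled from the text.

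The consequence depends on what was coded. If it was .034/.204, no power changes on this account. If it was OR = 5, the stated powers belong to a scenario the plan does not describe. Unless .204 itself was held, the flagged subgroup's control risk would then be nearer .15 to .16 than .20. The illustrative calculation puts the effect on SPI power at roughly 8 to 10 percentage points (56% against 48% or 46%). That size assumes an even 300/300 split and no clustering, and it should not be subtracted from the stated 96.4%. The point calls for clarification and correction; it does not show that the trial is underpowered.

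**What to change.** Check the simulation code and state in the Statistical power paragraph which quantities were set and which were derived.

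- If .034 and .204 were coded, restate the odds ratio as 7.3. The powers stand as far as this point goes.
- If OR = 5 was coded, print the risks actually simulated, for example about .037/.163 (overall .05, prevalence 10%) or .034/.150 (overall .046). If those were not the intended inputs, rerun the simulation and restate all three powers.

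In either case, give the prevalence of past-year attempts used for the 43,000 and for the 6,000, so that the overall risk can be checked.

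The cost is one corrected line and possibly a rerun of existing code. The downside is that the SPI power may come out lower, in which case the remark that it offsets incomplete SPI delivery would need to be revisited.

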For Aim 1, we will assess total number of subsequent attempts using the already-developed Mental Health Research Network (MHRN) algorithm for extracting MT suicide attempt information from claims data.^{10-12,48-58} The main effectiveness analysis is planned as a comprehensive model (i.e., including all 43,000 subscribers) evaluating Study 1 and Study 2 intervention effects, which provides optimal power and the ability to test interactive effects of interventions. All analyses will covary baseline (i.e., past year) values of dependent variables, and will use days incarcerated in the 6 months after the index jail release as an offset. **MT suicide attempts.** The main analysis framework will be logistic regression with the cumulative risk of a claims-data-identified suicide attempts requiring medical treatment over six months post-release as the outcome. We will secondarily use a negative binomial model and a count outcome for the number of MT suicide attempts. Our models will include robust standard errors due to clustering at the agency level. We will adjust for study month, and include indicator variables reflecting: (1) Study 1 intervention condition (i.e., CC or CAU); (2) inclusion in Study 2; (3) Study 2 intervention condition (i.e., RRT or Control). The ***hypothesis that the Study 1 intervention (CC) reduces suicide attempts*** is evaluated with magnitude and significance of parameter estimate associated with random assignment to the Study 1 intervention. The ***hypothesis that the Study 2 intervention (RRT) reduces suicide attempts*** is tested with the parameter estimate associated with exposure to the level 2 intervention. ***The hypothesis that the addition of flags and recommendations to provide SPI*** for individuals with past 12 months claims data identified suicide attempts (one component of the Study 2 intervention) ***will further reduce suicide attempts*** will be tested through the interaction between past history of suicide attempt and being in the Study 2 intervention condition. Identical analyses will be conducted for the other outcomes (all count outcomes): all cause injury and poisoning, outpatient BH visits, calls to CMS line, suicide-related ED visits/hospitalizations, and returns to jail detention. ***Exploratory.*** We will evaluate the interaction of Study 1 and Study 2 interventions by including an interaction term of the two indicators. ***Moderators.*** We will test sex, race/ethnicity, past suicide attempt (y/n), past 6-month BH visit (y/n), past 12-month arrest (y/n), area Deprivation Index,⁵⁹⁻⁶⁰ Mental Health Professional Shortage Area (HPSA)

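### The stated power for RRT (88.3%), SPI (96.4%) and CC (85.6%) does not follow from the plan's own inputs, which give about 21%, 56% and 73%

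*Combined protocol and SAP*

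**What the plan says.** The Statistical power paragraph of section C4 reports 2,001 simulation runs at a two-tailed 5% level with an intra-cluster correlation of .01. Its sample sizes are "We assumed 43,000 eligible subscribers for Study 1, with 50% randomly assigned to CC" and "we assumed 6,000 eligible subscribers for Study 2". About 10% of the latter, some 600, are expected to have an identifiable past attempt. The overall six-month risk is 0.05, split by past-year attempt as "034 in absence of past-year suicide attempt, 0.204 with a past-year suicide attempt, odd ratio (OR) = 5" (the first figure is .034).

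The results claimed are:

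- CC: "We will have 85.6% power to detect an effect equivalent to an OR of 0.89"
- RRT: "If we assume an intervention effect for Study 2 of 0.87 OR, we will have 88.3% power to detect this effect"
- SPI subgroup: "we will have 96.4% power to detect an OR of 0.63"

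The paragraph then treats the SPI power as a surplus that makes up for providers who may not deliver SPI. The Aim 1 analysis in section C4 says that the SPI hypothesis "will be tested through the interaction between past history of suicide attempt and being in the Study 2 intervention condition".

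**The concern.** The three figures conflict before any calculation. CC, with 43,000 subscribers and OR 0.89, is given 85.6%. RRT has almost the same odds ratio and the same baseline risk, about one seventh of the subscribers, and clustering by agency, yet is given more power (88.3%).

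The stake is how Study 2 will be read. If power is near 20%, the trial would miss its assumed RRT effect about four times in five, and a null result could be taken as evidence against the programme. The SPI figure is also used as reassurance about delivery, although the RRT Fidelity paragraph concedes that outreach attempts cannot be tracked at scale. Under section D3 the DSMB formally approves the analysis plan, so it would be approving these figures.

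**Working it through.** **Inputs.** From the Statistical power paragraph: 43,000 split 1:1 for CC; 6,000 for RRT; about 600 for SPI; risks .05 overall, .034 and .204; two-sided 5%. From section C2 (Training behavioral health providers): four cohorts start RRT at Months 4, 6, 8 and 10. Assuming even releases over 12 months and cohorts of equal size, exposed cohort-months are 9 + 7 + 5 + 3 = 24 of 48. That gives about 3,000 v 3,000 for RRT and 300 v 300 for SPI.

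**Who informs the RRT contrast.** The Aim 1 model holds all 43,000 subscribers but includes an indicator for being in Study 2. That indicator absorbs the difference between Study 2 and everyone else, so the RRT estimate comes essentially from the 6,000.

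**Formula.** Treated risk p1 comes from odds p0/(1 − p0) × OR. Then SE(log OR) = √[1/(n·p0(1 − p0)) + 1/(n·p1(1 − p1))], z = |ln OR|/SE, and power ≈ Φ(z − 1.96). This ignores clustering and the study-month adjustment. For RRT and SPI, leaving out month adjustment favours the plan.

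| Test | n per arm | p0 v p1 | ln OR | SE | z | Power | Stated |
|---|---|---|---|---|---|---|---|
| CC, OR 0.89 | 21,500 | .0500 v .0447 | −0.117 | 0.0455 | 2.56 | 72.7% | 85.6% |
| RRT, OR 0.87 | 3,000 | .0500 v .0438 | −0.139 | 0.122 | 1.14 | 20.6% | 88.3% |
| SPI, OR 0.63 | 300 | .204 v .139 | −0.462 | 0.220 | 2.10 | 55.6% | 96.4% |

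A pooled-variance two-proportion test gives 72.7%, 20.6% and 56.0%.

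**What the stated power would need.** For RRT, n per arm = (1.96 + 1.19)² × (1/.0475 + 1/.0419)/0.139² ≈ 23,000, or about 46,000 against the 6,000 available. SPI needs about 1,900 against 600, and CC about 59,700 against 43,000. At the plan's own sample sizes, the stated powers correspond to ORs of 0.66 (RRT), 0.41 (SPI) and 0.87 (CC). The ORs detectable with 80% power are 0.70, 0.53 and 0.88.

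**Attempts to rescue the figures.**

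- *Event rate of 50%:* RRT 77%, SPI 80%.
- *Exposed share of 30% to 70%:* RRT 18% to 21%, SPI 46% to 56%.
- *One-sided test, contrary to the text:* RRT 31%, SPI 68%, CC 82%.
- *All 6,000 treated as exposed against the other 37,000:* RRT 54% to 58%, depending on the variance formula.
- *RRT and SPI effects combined across the 6,000:* 48% to 61%.
- *Monte Carlo error with 2,001 runs:* at most 1.96 × √(.856 × .144/2,001) = 1.5 points.

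**Simulation.** Stepped-wedge simulations of the 12 agencies within the 43,000-subscriber logistic model, with study month, past attempt, the Study 2 indicator and ICC 0 or .01, gave about 17% to 23% for RRT. They gave about 65% to 73% for CC and 50% to 59% for the SPI subgroup effect.

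**The SPI test actually planned.** An interaction compares the log OR in the 600 with that in the other 5,400 (2,700 per arm, risk .034). The variance for the 600 is 0.0484.

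- If RRT has OR 0.87 in the others, their variance is 0.0241. SE = √0.0725 = 0.269, z = ln(0.87/0.63)/0.269 = 1.20, power 22%.
- If RRT has no effect in the others (OR 1.0), their variance is 0.0226. SE = √0.0709 = 0.266, z = 0.462/0.266 = 1.73, power 41%.

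**The risk inputs.** (.204/.796)/(.034/.966) = 7.28, and .204/.034 is a risk ratio of 6. The risks do agree with the overall figure: 0.9 × .034 + 0.1 × .204 = .051. An OR of 5 with overall risk .05 and 10% prevalence would need about .037 and .163, which lowers SPI subgroup power to about 48%.

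**The case against.** The plan's figures come from a simulation whose code, exposure definition and spread of cluster sizes are not printed, so the cause of the discrepancy cannot be established. That is correct. Some unstated inputs come close:

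- OR 0.87 applied to all 43,000 split 1:1, with average risk .05, gives 88.2%.
- All 600 flagged subscribers exposed, against about 3,700 past attempters outside Study 2 (assuming 10% prevalence there), gives 95.9%.
- A baseline risk near .07 gives about 85% for CC.

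The first two contradict the described design and the third contradicts the stated risk. They suggest where to look and do not support the figures.

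The CC gap is also much smaller, about 13 points, equivalent to OR 0.87 in place of 0.89, and the plan expects stronger CC effects than that. This stands: the CC correction does not threaten Study 1.

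The SPI population is not described consistently. Weekly reports flag any lifetime attempt, whereas the analysis and the risk inputs refer to the past 12 months. With 1,200 flagged, subgroup power would be about 85%, still below 96.4%.

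Finally, sample size does not depend on this calculation, since Study 1 takes every eligible release and Study 2 the 12 largest agencies. Nor does the plan say that a null result will be read as no effect. Both are fair. They limit the consequences to the stated power and to interpretation, but do not make the figures right.

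**Conclusion.** The concern holds. At the plan's stated effects, power is about 21% for RRT (17% to 23% in simulation), about 56% for the SPI subgroup (50% to 59%) and about 73% for CC (65% to 73%). The plan claims 88.3%, 96.4% and 85.6%. The RRT error is decisive and no reading of the stated inputs closes it. The SPI figure is both too high and for a different test from the one planned, whose power is about 22% to 41%. The CC error is real but secondary. The printed OR of 5 is inconsistent with its own risks.

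The closed-form results assume half of Study 2 exposed, even releases and a control-group risk of .05 (.204 in the flagged group). They omit clustering, month adjustment and the days-incarcerated offset. The conclusion survives the ranges tried for exposed share and event rate.

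**What to change.** 1. Correct and re-run the simulation on the planned Aim 1 model. State the exposed share, cluster sizes and baseline risks used, and print what it gives. The closed-form values above are a guide to what to expect: about 73% for CC, 20% for RRT and 55% for the SPI subgroup at the stated ORs.
2. Add the ORs detectable with 80% power (about 0.88, 0.70 and 0.53 by the same approximation) and separate power for the SPI interaction.
3. Reconcile the risks .034 and .204 with the printed OR of 5. State whether the flagged group is defined by lifetime or past-year attempts.
4. Delete the sentence that relies on surplus SPI power to offset incomplete delivery.
5. State that a non-significant RRT or SPI result will be reported as an estimate with its confidence interval, not as absence of effect.

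The cost is a re-run of an existing simulation and revised text for the DSMB. No subscribers or agencies are added, and enrolment and allocation do not change. The price is a less favourable statement of what Study 2 can detect.

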Aim 4. Identify and define implementation outcomes and processes to guide future implementation trials. In line with common implementation data elements and activities, we will conduct systems analysis and improvement (e.g., process mapping and cascade analysis), keep and analyze implementation documentation, and collect and analyze pilot implementation measures. This will allow us to: (1) optimize scalability and sustainability of the interventions, and (2) identify implementation strategies that maximize scalability and sustainability to inform future research.

B. Background

More than 10 million people are arrested and booked into jails each year in the U.S.¹ Half (40-50%) report lifetime suicide ideation or behavior, 13-20% have attempted suicide, and suicide is a leading cause of death in the months after jail release (18 times the general population).²⁻⁶ Those who end up in jail are often from vulnerable groups among the highest risk for suicide, such as young males, persons with mental health and substance use disorders, socially disenfranchised, and those who have previously engaged in suicide behaviors.⁷ Given that ~10% of all suicides with known causes in the U.S. occur in the context of a recent criminal or legal stressor (often arrest and jail detention)^{8,9} targeting suicide risk after jail detention could have a noticeable impact on national suicide rates.

Individuals are most likely to be arrested when acutely ill (i.e., manic or psychotic), but arrest and jail detention often exacerbate symptoms of mental illness and destabilize medication and other treatment regimens.¹⁰⁻¹² Unfortunately, few of the ~3,100 U.S. jails have adequate staff to fully address health needs of individuals at risk for suicide, including basics like service linkage. Post-release outcomes are poor.¹³⁻²⁵ Among community mental health-affiliated individuals with serious mental illness, only one-third engage in an anticipated treatment service following jail release.²⁷ In fact, for many (45%), the next mental health treatment received was in jail.²⁶ Both health and jail providers want better linkage between systems to provide service continuity and reduce unnecessary morbidity and mortality.^{10,27-34}

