RRT Fidelity. We will be able to electronically track whether reports go out and whether they are timely/accurate. In addition, although we do not have a scalable way to track outreach attempts for 6,000 subscribers in Study 2, we will carefully document implementation processes and meet monthly with CareSource and intervention agencies, hear their experiences, offer feedback, and help problem-solve challenges. We will keep structured implementation process notes from these meetings for further analysis. Provider names will be included in the notes. All data from the implementation process feedback will be securely stored in REDCap. No names or identifiers will be used in any published works and will be accessible only to authorized research staff. Testing our service engagement mechanism will also help to elucidate steps in the causal chain (i.e., from the reports, to services provided, to suicide attempts).

Assignment to “intervention” and “control” conditions in the two studies is independent: participants may receive Intervention-Intervention, Intervention-Control, Control-Intervention, or Control-Control. Participants will be followed for 6 months following jail release using claims data.

C4. Data Analysis

Twelve months of historical (i.e., prior to arrest) and six months of prospective (i.e., after release) jail and Medicaid claims data will be extracted from CareSource’s Jail-Medicaid database for each participating subscriber for all measures, including demographics, diagnoses, suicide attempts, service use, number of arrests, dates of jail bookings/releases, and days incarcerated. Each eligible subscriber will be followed for 6 months following the index release from jail using claims data. CareSource will provide a limited dataset to the P50 Center (at MSU) that will be de-identified and analyzed by Center statisticians. Because these statisticians are employed by Brown University, an IAA will be established with both MSU and Brown University.

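### Surplus power covers only modest non-delivery of SPI: even taking 96.4% as given, it falls to 80% at about 23–25% non-delivery (about 36% if the general RRT effect persists), and SPI completion is not recorded per client

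*Combined protocol and SAP*

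**What the plan says.** The power paragraph of section 2, C4 (Data Analysis) reports a simulation with about 6,000 Study 2 subscribers. On prior attempts it says "We expect that ~10% of the 6,000", giving about 600, will have one identifiable in claims. For those with a past-year attempt it says "we will have 96.4% power to detect an OR of 0.63 (the OR detected for SPI in our previous trial, SPIRIT"). The test level is given as "Significance was assessed using a two-tailed type-I error level of 5"%. It then concludes: "Having superadequate power for this test offsets concerns about providers potentially not providing SPI as instructed in this large, real-world study". No non-delivery rate is stated, and no power figure is shown under partial delivery.

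Earlier in C4, the SPI component is tested by the interaction of past attempt with Study 2 condition. The tested exposure is therefore being flagged at an agency in its RRT period, not receiving SPI.

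On delivery, RRT Fidelity in C2 says the sending, timeliness and accuracy of reports are tracked, but "we do not have a scalable way to track outreach attempts for 6,000 subscribers in Study 2". Monthly meetings produce structured process notes. The outcome list in C2 includes outpatient behavioral health visits but not SPI. Section 3.A names three data sources: focus-group input, process notes with provider feedback, and claims.

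**The concern.** An OR of 0.63 is described as the effect found for SPI in the investigators' earlier trial. In this trial a flagged client who is not reached, or is seen but not given SPI, still counts as exposed. Each such client moves the expected OR towards 1, or towards the general RRT effect. High power at 0.63 is not high power at the diluted OR, so whether the surplus is enough depends on how much non-delivery occurs. The plan neither states nor bounds that quantity.

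The reading of a null is at stake. If the interaction is not significant, the sentence invites the conclusion that patchy delivery had been allowed for. Without client-level SPI completion, that conclusion could not be checked.

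**Working it through.** **Inputs from C4.** Two-sided 5% level; power 96.4% at OR 0.63; six-month risk 0.204 with a past-year attempt; RRT effect OR 0.87.

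**Can 96.4% be reproduced?** Not from the printed inputs. Cohorts start at months 4, 6, 8 and 10, giving 9 + 7 + 5 + 3 = 24 of 48 cohort-months exposed. With even releases (an assumption) that is about 300 flagged clients against 300. Risks of 0.204 and 0.139 (OR 0.63) then give about 56% power. A rough 300-replicate simulation of the full 43,000-person model gave about 71% for the subgroup effect and 65% for the interaction, each within 5–6 points. The plan's simulation code is not printed, so this is a failure to reproduce and not a demonstrated error. The rest accepts 96.4%.

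**Implied standard error.** −ln 0.63 = 0.462. The signal at 96.4% power is 1.960 + 1.799 = 3.759, so SE = 0.462 / 3.759 = 0.1229.

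**Effect needed for 80% power.** (1.960 + 0.842) × 0.1229 = 0.344 on the log scale, or OR 0.709.

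**Dilution.** Let f be the share of flagged, exposed clients who do not get SPI. Power = Φ(effect / 0.1229 − 1.960). Two ways of mixing were used:

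- Log-odds: effect = (1 − f) × 0.462 + f × b, where b = 0 (no benefit without SPI) or b = −ln 0.87 = 0.139 (RRT effect kept).
- Risk: mixed risk = (1 − f) × 0.139 + f × r, where r = 0.204 (no benefit) or r = 0.182 (OR 0.87 applied to 0.204), converted to an OR against 0.204.

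**Non-delivery at which power reaches 80%.**

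- No benefit, log-odds: 1 − 0.344/0.462 = 25.5%.
- No benefit, risk: OR 0.709 is a risk of 0.1537, and (0.1537 − 0.1390)/(0.2040 − 0.1390) = 22.6%.
- RRT effect kept, log-odds: (0.462 − 0.344)/(0.462 − 0.139) = 36.5%.
- RRT effect kept, risk: (0.1537 − 0.1390)/(0.1823 − 0.1390) = 33.9%. Letting the SE change with the mixed risk, by a two-proportion calculation sized to give 96.4%, moves this to 36.1% and the 22.6% to 24.1%.

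**Power (%) by non-delivery, log-odds / risk mixing, SE fixed.**

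| Non-delivery | No benefit without SPI | OR 0.87 kept |
|---|---|---|
| 0% | 96.4 / 96.4 | 96.4 / 96.4 |
| 10% | 92.3 / 91.4 | 93.8 / 93.4 |
| 20% | 85.3 / 82.8 | 89.9 / 89.0 |
| 30% | 74.9 / 70.7 | 84.4 / 82.9 |
| 40% | 61.6 / 56.2 | 77.3 / 75.1 |
| 50% | 46.8 / 41.2 | 68.7 / 66.1 |

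Example at 50%, no benefit, log-odds: 0.5 × 0.462 = 0.231; 0.231/0.1229 = 1.880; Φ(1.880 − 1.960) = 46.8%.

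**Which column fits the planned test?** In the interaction, the general RRT effect cancels. A flagged client without SPI who gains OR 0.87 looks like an unflagged client and adds nothing. The interaction effect is then (1 − f) × (0.462 − 0.139), which shrinks in proportion to delivery. If 96.4% is the power of that test, 80% is reached at the same 25.5%. If 96.4% is for the overall effect within the flagged subgroup, as its wording suggests, the second column can apply.

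**Scale of a delivery record.** 600 / (12 agencies × 12 months) = 4.2 flagged clients per agency-month, assuming an even spread.

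**The case against.** The strongest defence is that the sentence is partly right. It says surplus power offsets a concern, not that power survives any level of non-delivery. At 20% non-delivery power is still 83–85% with no residual benefit and 89–90% with the RRT effect kept. A reader might infer that the statement is simply wrong; the figures do not support that. The plan also sets no target power, so the 80% line is a convention brought by this review. That stands.

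RRT also gives clients more than SPI: release notification, re-engagement and a risk-assessment reminder. For a within-subgroup effect the more generous column is a fair reading. If the 0.63 came from a trial with incomplete delivery, some dilution is already in it; the documents do not say. Both points stand as stated assumptions.

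A reader might take the Background statement that "only one-third engage in an anticipated treatment service following jail release" as the expected SPI delivery rate. It is not. It describes people with serious mental illness under existing care, and RRT is meant to raise engagement. It shows only that large non-delivery is conceivable.

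A reader might also infer that delivery goes wholly unobserved, or that non-delivery would be the likeliest cause of a null. Neither is supported. Outpatient claims are an outcome and a mediator, and can show flagged clients with no billed visit. Process notes and the planned cascade analysis add agency-level information. No section ranks reasons for a null, and limited sample size is an obvious rival.

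What these sources cannot show is whether a given flagged client who was seen received SPI.

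**Conclusion.** The offset claim is unquantified and holds only for modest non-delivery. Conditional on 96.4% at OR 0.63, and on that OR reflecting full delivery, the margin down to 80% power is about 23–25% non-delivery if clients without SPI gain nothing. That is the relevant case if 96.4% is the power of the interaction test. The margin is about 36% (34% on the less favourable mixing) if those clients keep OR 0.87. At half delivery, power is 41–47% or 66–69%.

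A reader might go further and infer from the failure to reproduce 96.4% that there is no surplus at all. The documents do not settle that, because the simulation code and the exact contrast behind the figure are not given. It is a separate question, although a lower true power would shrink the margin.

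Because SPI completion is not captured per client, actual delivery cannot be placed on this scale after the trial. A null would speak to the strategy of flagging clients and recommending SPI, which is what C4 tests, and not to SPI itself.

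**What to change.** 1. In the power paragraph of C4, replace the sentence with power for the flag test over a stated range of delivery rates, under both assumptions (no benefit without SPI; RRT effect of OR 0.87 kept). State whether 96.4% refers to the interaction or to the effect within the flagged subgroup. The cost is a short re-run of the existing simulation and a less favourable figure.

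2. State in C4 that a null result bears on the flag-and-recommendation strategy and is not evidence against SPI unless delivery is shown.

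3. Where data and privacy arrangements allow, have agencies return SPI completed (yes/no) and date, for flagged clients only, through the insurer so that analysts receive it de-identified. This is a data source beyond the three in section 3.A, which also rests the status of subscribers on de-identified claims alone, so it needs privacy and IRB review. The burden is about 4 entries per agency-month on the past-year definition.

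4. Reconcile the flag definition. Weekly reports in C2 flag any lifetime attempt found in available claims, whereas the hypothesis and power subgroup in C4 use the past 12 months. Under the lifetime definition the number of flagged clients and the reporting burden would be larger, and the power subgroup would not be the flagged group.
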